2. Study Objectives: The objective of this study is to investigate the neural mechanisms of gait adaptation and the effects of transcutaneous electrical nerve stimulation (TENS) on adaptability during split-belt treadmill training in PwMS. Functional near-infrared spectroscopy (fNIRS) will be used during a split-belt treadmill training paradigm to assess cortical activation during gait adaptation. Additionally, the effect of split-belt treadmill training coupled with TENS on gait adaptability in PwMS will be tested with active and inactive TENS during split-belt treadmill sessions. Cortical activation and the effect of TENS on gait adaptability will be compared between neurotypical adults and PwMS to assess differences that can be attributed to multiple sclerosis. Specifically, we hypothesize that the sensorimotor integration areas of the cortex including the supplementary motor areas (SMA), premotor cortex (PMC), somatosensory cortex (S1), and posterior parietal cortex (PPC) will have heightened activity during split-belt treadmill training, compared to when the belts are moving the same speed. Additionally, we hypothesize that the application of TENS during split-belt treadmill training will significantly increase gait symmetry improvements when compared to split-belt treadmill training alone and will also result in improved adaptation retention.

B. Background and Significance

1. Study Significance: Studies have consistently demonstrated that split-belt treadmill training can acutely improve gait symmetry, however there is minimal application of this paradigm toward enhancing or prolonging these improvements. The impact of this study is not only revealing the cortical mechanisms of sensorimotor adaptation and improving gait symmetry, but a necessary step towards translating these improvements out of the lab into a real-world environment thereby persistently improving mobility for not only PwMS but the tens of millions of individuals who experience gait dysfunction.

INSTITUTIONAL REVIEW BOARD NON-EXEMPT PROTOCOL TEMPLATE

2. Our recent studies showed robust gait symmetry improvements in PwMS following split-belt treadmill training and additionally has demonstrated that TENS improves positional awareness and motor learning during a stepping task. The combination of these findings leads us to want to investigate the neural mechanisms of split-belt treadmill training and if TENS can enhance to effects of split-belt treadmill training.

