A. Study Type and Design: This is a crossover study with both PwMS and age and sex-matched neurotypical controls. 30 PwMS and 20 neurotypical controls be randomized into two groups and will participate in two split-belt treadmill training sessions while outfitted with cortical fNIRS and TENS devices on their bilateral tibialis anterior and rectus femoris. The first group will complete split-belt treadmill training with TENS OFF during the first visit and TENS ON during the second visit. The second group will complete split-belt treadmill training with TENS ON during the first visit and TENS OFF during the second visit to control for a learning effect. In between visits there will be a 4-week washout period. Participants will receive TENS only during the 10-minute split-belt adaptation period of the paradigm. During all other periods the TENS will be OFF.

B. Sample size, statistical methods, and power calculation

1. Total number of subjects who will be approached (including screen fails, controls and subject withdrawals) to reach enrollment numbers for the lifetime of the study for this investigator's site: 60
2. Total number of subjects to be enrolled at this site: 50

INSTITUTIONAL REVIEW BOARD NON-EXEMPT PROTOCOL TEMPLATE

3. Brief Description/justification for the proposed sample size in *lay terms*: From our preliminary data we computed a large effect size of 1.01 for change in brain activity in the SMA from baseline walking to split-belt treadmill training. According to our power analysis, to maintain an alpha of 0.05 and a power of 0.8, at least 10 participants per group are needed to detect significant changes in brain activity.
4. Simple randomization will occur (TENS first or TENS second) for both groups (PwMS and neurotypical controls).
5. No masking will occur in this study.

C. Subject Criteria (See Vulnerable Populations appendix 1, if applicable): PwMS and neurotypical controls from ages 18-86. All races and genders are included.

1. Inclusion criteria:

- A diagnosis of relapsing remitting multiple sclerosis OR a neurotypical adult (ages 18-86)
- Not experiencing an active relapse
- Able to stand and walk without an assistive device
- Able to walk for three tenths of a mile without stopping to rest
- MS participants must have a neurologist confirmed diagnosis of relapsing-remitting MS.
- MS participants must be independently ambulatory in the community, expanded disability status scale (EDSS) score < 5 (clinical measure of MS severity).

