- **Cortical Activation via fNIRS.** All fNIRS data will be acquired using a mobile NIRS Sport2 device (NIRx Medical Technologies, nirx.net), which will be secured to participants' backs using backpack-like straps and buckles. This head probe was designed to measure regions of interest (ROI) that were established a priori. The Juelich atlas within the fNIRS Optodes Location Decider (fOLD) toolbox in MATLAB was used to design our optode montage which identifies channel locations above superficial components of the frontal, motor, and sensory regions. Our fNIRS head probe will include 16 sources and 15 detectors which will create 48 channels over the designated ROIs (Figure 1). Additionally, eight short-separator detectors will be used to measure scalp perfusion. All fNIRS data will be acquired and streamed to a laptop using Aurora software v.2021.9 (NIRx Medical Technologies, nirx.net/aurora). Raw fNIRS data will be processed using a commercial software tool, Satori v.1.8 by Brain Innovation (NIRx Medical Technologies, nirx.net/satori) to perform pre-processing steps, such as motion artifact removal, physiological noise detection, and channel selection and removal. Following, the raw light intensity data will be converted to optical density values and then converted to oxygenated hemoglobin (HbO), deoxygenated hemoglobin and total hemoglobin values using the Modified Beer-Lambert Law automatically through Satori software. The HbO beta values calculated from general linear models will be used as a proxy for cortical activity, and we will measure changes in HbO beta between each protocol period described in Figure 2B.

[figure not shown]

Figure 1. Optode montage (16x15) created using Brodmann atlas within fOLD to allow measurement of cortical hemodynamics for premotor, sensorimotor, and posterior parietal regions. Each red circle indicates a source optode, each blue circle represents a detector optode, and each purple connecting line represents a unique channel.

2. Study Procedures:

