- **Split-belt Treadmill Training Paradigm.** The participants will be outfitted with 6 APDM Opal inertial sensors (APDM Inc, Portland, OR) as well as 16 retroreflective markers for collection of three-dimensional motion capture data during a 10-minute split-belt treadmill training paradigm (Figure 2). For the overground walking portion, participants will be asked to walk back and forth down a 30m hallway for 2 minutes while APDM Mobility Lab is collecting inertial sensor gait cycle parameters. For the treadmill portion, participants will be asked to walk on a custom-built instrumented,

INSTITUTIONAL REVIEW BOARD NON-EXEMPT PROTOCOL TEMPLATE

split-belt treadmill with two Bertec force platforms (Model 4060-10, Bertec Corp, Columbus, OH) consisting of two separate belts, each with its own motor that permits the speed of each belt to be controlled independently and collects ground reaction forces at 1000 HZ. The speed at which a participant is walking will be individualized to their overground preferred walk speed and fast walk speed. Specifically, during the tied-belt walking period, the belts will be set to the overground preferred walking speed. During split-belt treadmill adaptation period, the “fast belt” speed will be equal to the participant’s fast walk speed while the “slow belt” speed will be one half of the participants fast walk speed (2:1 ratio). Prior

[figure not shown]

Figure 2. (Top) Time course for the split-belt treadmill training paradigm depicting the stages of baseline, adaptation, and deadadaptation (**Top**) fNIRS block design collection protocol. Following a 1-minute baseline rest period, fNIRS will be collected during tied-belt walking, split-belt treadmill training, and deadadaptation utilizing an average of two 30-second blocks for each period of the paradigm to assess differences in activation between each period.

research has determined that the “fast belt” speed should be set for the more affected leg to improve gait asymmetry. Following the adaptation period, a 10-minute deadadaptation period with the belts tied at the preferred speed will occur to monitor gait symmetry changes during deadadaptation between groups.

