- **TENS Protocol.** 30 PwMS and 30 age- and sex- matched controls will be randomized into two groups and complete two split-belt treadmill training sessions identical to Aim 1, while outfitted with cortical fNIRS and TENS devices on their bilateral tibialis anterior and rectus femoris. The first group will complete split-belt treadmill training with TENS OFF during the first visit (these are the participants in Aim 1) and TENS ON during the second visit. The second group will complete split-belt treadmill training with TENS ON during the first visit and TENS OFF during the second visit to control for a learning effect. In between visits there will be a 4-week washout period (Figure 3). Participants will receive TENS only during the 10-minute split-belt adaptation period of the paradigm. During all other periods the TENS will be OFF. We will use an FDA-approved clinical TENS device, the LG-TECELITE Therapy System (LGMedSupply, Cherry Hill, NJ). Stimulation will consist of bursting biphasic pulses delivered with electrode pairs (2 in. \times 4 in. pads) placed on the skin over the

INSTITUTIONAL REVIEW BOARD NON-EXEMPT PROTOCOL TEMPLATE

stimulated muscles. The stimulus frequency will be set at 5 Hz with a seven pulses of 0.15 ms based on recent evidence suggesting that bursting TENS is most effective for improving walking performance and limits nerve accommodation to the stimulation. The amplitude of the TENS stimulation will be individualized for each participant in accordance with their specific motor threshold. The TENS amplitude will be slowly increased at 1 mA increments on each individual muscle until non-voluntary muscle contractions can be seen or felt by the investigator, then the amplitude will be set to 2 mA below the motor threshold for each muscle and limb during the split-belt adaptation period. Additionally, we are choosing to outfit TENS on the tibialis anterior and rectus femoris due to previous studies successfully improving gait performance in PwMS using these stimulation locations (Figure 3).

[figure not shown]

Figure 3. (Left) Study design schematic including randomization and TENS condition at each visit. (Right) Example of TENS electrode placement on the bilateral tibialis anterior and rectus femoris.

- **Clinical Assessments**

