- C. Statistical Analysis Plan:** In this crossover design, PwMS and healthy control participants will be pseudo-randomized to begin in either the TENS First or TENS Second condition. Randomization will be performed using a random number generator and will be counterbalanced across age, sex, and fast limb to ensure group balance. A predefined list of participant numbers with corresponding randomized assignments will be generated prior to enrollment. Linear mixed-effects models will be used to identify differences in adaptation and fNIRS outcomes, with group (PwMS vs. healthy controls), visit (Visit 1 vs. Visit 2), and TENS condition (TENS ON vs. TENS OFF), along with their interactions, as fixed effects, and participant number as a random effect. Assumptions of linearity, normality of residuals, and homoscedasticity will be tested for each model. Following model creation, a repeated measures ANOVA will be performed for each adaptation outcome (adaptation rate and adaptation savings) and for cortical activation (HbO beta). Type III ANOVAs with Satterthwaite's method for degrees of freedom estimation will be used for all analyses. Post-hoc comparisons will be conducted using estimated marginal means (EMM) to further investigate significant main effects and interactions. P-values will be corrected using the Benjamini–Hochberg false discovery rate within each outcome and group when applicable. Cohen's d will be calculated to quantify effect sizes. Separate regression models will be conducted to assess the influence of demographic covariates on primary outcome models. All statistical analyses will be conducted using the lme4 and emmeans packages within R and were two-tailed with an alpha threshold set at 0.05.

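### TENS is on only while the belts are split, so the split-versus-tied HbO contrast should be tested on TENS OFF visits, which the SAP does not specify

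*Combined protocol and SAP*

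**What the plan says.** **Hypothesis.** Study Objectives (I.A.2) predicts that SMA, PMC, S1 and PPC "will have heightened activity during split-belt treadmill training, compared to when the belts are moving the same speed". This is a within-person comparison of two walking periods. The TENS hypotheses in the same section concern gait symmetry and retention of adaptation, not cortical activity.

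**Stimulation.** Section II.A, repeated under TENS Protocol in III.D.2, says "Participants will receive TENS only during the 10-minute split-belt adaptation period of the paradigm" and "During all other periods the TENS will be OFF". Under TENS Protocol, "the amplitude will be set to 2 mA below the motor threshold for each muscle and limb".

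**Cortical measurement.** The Figure 2 legend says that "fNIRS will be collected during tied-belt walking, split-belt treadmill training, and deadadaptation". The same legend reports each of these periods as a mean over two half-minute blocks. The fNIRS paragraph of III.D.1 says "we will measure changes in HbO beta between each protocol period described in Figure 2B".

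**Analysis.** Section V.C specifies one mixed-model form for the adaptation and fNIRS outcomes, with group, visit and "TENS condition (TENS ON vs. TENS OFF), along with their interactions, as fixed effects", and a random effect for participant. Protocol period is not among the listed terms. Nothing there limits the cortical analysis to TENS OFF visits. The only related remark is an aside under TENS Protocol that identifies the OFF-first participants as those in Aim 1.

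**The concern.** On an ON visit the belts split and the stimulator starts together, and they end together. No period has stimulation with tied belts. S1 and PPC are among the hypothesised regions, and the protocol itself presents TENS as sensory augmentation, so a cortical response to the stimulation is plausible. The short-separator channels measure scalp perfusion and would not remove such a response.

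Two results are exposed. First, a split-versus-tied estimate averaged over ON and OFF visits would carry part of the stimulation response into the test of the main cortical hypothesis. Secondly, the ON-minus-OFF difference in HbO during split-belt walking contains both the response to stimulation and any change in adaptation-related activity. Enrolling more participants separates neither, because the two coincide in every ON session.

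**Working it through.** **Inputs.** Effect size 1.01 for the SMA change from baseline to split-belt walking, alpha 0.05, power 0.80 and at least 10 per group (II.B.3). Two-tailed tests (V.C). 30 PwMS and 20 controls (II.A). TENS Protocol gives 30 controls; the two figures need reconciling, and the smaller is used here.

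**Reproducing the plan's figure.** A two-sided paired t-test with noncentrality d√n gives power 0.756 at n = 9 and 0.811 at n = 10 for d = 1.01. The stated 10 is reproduced, so it is the size for a within-person period contrast. A two-sample t-test would need 17 per group.

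**What each contrast estimates.** Let A be the split-minus-tied HbO change without stimulation. Let τ = e + D be the total TENS effect on HbO during split-belt walking, where e is the direct response to stimulation and D is any change in adaptation-related activity.

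| Contrast | Expected value |
|---|---|
| Split − tied, OFF visit | A |
| Split − tied, ON visit | A + τ |
| Mean of the two visits | A + τ/2 |
| ON visit − OFF visit | τ = e + D |

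The OFF visit isolates A. No combination of the recorded periods isolates e or D during adaptation.

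**Size.** The documents give no τ. As an assumption, take τ = 0.2, 0.5 and 0.8 SD of the within-person change. The shift in the mean of the two visits, τ/2, is then 0.10, 0.25 and 0.40 SD. With A = 1.01 the averaged estimate is 1.11, 1.26 and 1.41, and the ON-visit estimate is 1.21, 1.51 and 1.81. A negative τ would shift them downwards by the same amounts.

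**Chance of a significant split-versus-tied result when A = 0** (two-sided paired t at 0.05):

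| n | Data used | τ = 0.2 | τ = 0.5 | τ = 0.8 |
|---|---|---|---|---|
| 30 | ON visit only | 0.19 | 0.75 | 0.99 |
| 20 | ON visit only | 0.14 | 0.56 | 0.92 |
| 30 | Mean of both visits | 0.08 | 0.26 | 0.56 |
| 20 | Mean of both visits | 0.07 | 0.19 | 0.40 |

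The last two rows keep the single-visit SD. Averaging normally reduces it, which would raise these figures.

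**Power from OFF visits alone, d = 1.01.** Each completer supplies one OFF visit.

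- n = 20: noncentrality 1.01 × √20 = 4.52, power 0.99.
- n = 30: noncentrality 1.01 × √30 = 5.53, power above 0.99.
- OFF-first participants only, about 10 controls and 15 PwMS if the sequences split evenly: power 0.81 and 0.95.

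At a smaller effect of 0.5 (an illustration; the plan states none for the other regions), OFF-visit power is 0.56 for n = 20 and 0.75 for n = 30. None of these figures allows for the FDR correction.

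**The case against.** The strongest reply has four parts.

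- **The SAP does not prescribe pooling.** It fits TENS with its interactions and uses estimated marginal means, so OFF-condition estimates can be obtained, and the Aim 1 aside points to unstimulated data. This stands in part: a clean test is available. But V.C does not say that it will be the test, a main effect from the listed model averages over TENS conditions, and the aside would use only about half the OFF visits.
- **ON minus OFF is not biased for every question.** If sensory input is how TENS is meant to work, the difference during split-belt walking is a valid total effect. This stands. It is ambiguous only when read as a change in adaptation activity alone.
- **The mechanistic misreading is not in the plan.** A reader might infer that the SAP takes the TENS term in HbO as proof that TENS alters the cortical mechanism of adaptation. V.C gives no such interpretation, and the TENS hypotheses concern gait. The case for a labelling rule is preventive.
- **The size is unknown.** The range for τ is assumed, the stimulation is below motor threshold, and 1.01 is an SMA effect, whereas the most plausible direct response is in S1 and PPC. This also stands, so the figures show sensitivity and do not estimate actual bias.

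**Conclusion.** The concern holds for the cortical outcome. As written, the SAP lets the split-versus-tied test draw on ON visits, where the estimate is A + τ, and an average over visits is off by τ/2. That is 0.1 to 0.4 SD over the assumed range of 0.2 to 0.8, in a direction that the documents do not fix. The structure follows directly from the stimulation schedule; only the size rests on assumption.

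Three stronger inferences are not supported. The main cortical hypothesis is not untestable, because every completer gives an unstimulated visit. The stated sample size is not wrong on this account. The gait outcomes are not affected, because adaptation rate is measured within the split-belt period and compared ON with OFF, and savings are derived from those rates, so no unstimulated reference period enters.

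**What to change.** Change the SAP only, before the HbO data are analysed:

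1. Add protocol period and its interaction with TENS to the HbO model.
2. State that the split-versus-tied cortical hypothesis is tested on the TENS OFF visits of both sequences, with visit as a factor. Among OFF visits, visit coincides with sequence, so this factor also takes up any carry-over from an earlier ON visit.
3. Report the ON-minus-OFF HbO difference during split-belt walking as the total effect of TENS (stimulation response plus any change in adaptation activity), not as evidence that TENS changed the cortical mechanism of adaptation.
4. Optionally add deadaptation minus tied-belt baseline, ON versus OFF, as a supportive analysis. The stimulator is off in both periods, but the contrast measures an after-effect, not activity during adaptation, and so should not lead.

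The cost is one visit per person instead of two in the main cortical test. At the SMA effect that loss is negligible. For regions with smaller effects, or after FDR correction, power will be lower, and the SAP should acknowledge this. No new data collection is needed.

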- 3 Trained graduate students and the principal investigator will determine whether the subject is able to give consent. People with cognitive impairments and minors will be excluded from this study due failing to meet the inclusion/exclusion criteria.

D. Specific procedures and techniques used throughout the study

1. Laboratory tests
 - **Gait Adaptation.** This will be assessed using inertial sensors and 3-D motion capture. Both use noninvasive markers that are placed on the lower limbs of the participants. Our outcome measures assessing gait adaptation will be step length asymmetry (SLA). Step length is quantified by the anterior-posterior distance between heel markers at leading limb heel strike. Step length asymmetry will be calculated by subtracting the step length of the less affected limb from the step length of the more affected limb for each consecutive step and normalized to participant stride lengths and will be assessed continuously throughout each gait trial. We will use step length asymmetry to identify 1) the adaptation rate during the split-belt adaptation period to assess speed of adaptation between conditions and groups, and 2) adaptation savings, or the difference in adaptation rate between visit 2 and visit 1, to quantify adaptation retention between conditions and groups.

INSTITUTIONAL REVIEW BOARD NON-EXEMPT PROTOCOL TEMPLATE

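### Adaptation savings has one value per participant, so the mixed model the SAP assigns to it cannot be fitted; the allocation rule also needs one reconciled statement

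*Combined protocol and SAP*

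**What the plan says.** **Savings.** Section III.D.1 (Gait Adaptation) describes "adaptation savings, or the difference in adaptation rate between visit 2 and visit 1", and uses it to measure retention. Better retention under TENS is one of the hypotheses in section I.A.2. Section V.C (Statistical Analysis Plan) sets out linear mixed models with group, visit and TENS condition, "along with their interactions, as fixed effects, and participant number as a random effect". It then says that "a repeated measures ANOVA will be performed for each adaptation outcome (adaptation rate and adaptation savings", with cortical activation handled the same way. No other model for savings is given.

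**Allocation.** Section II.B.4 reads "Simple randomization will occur (TENS first or TENS second) for both groups (PwMS and neurotypical controls". Section V.C calls the allocation pseudo-randomised and says "Randomization will be performed using a random number generator and will be counterbalanced across age, sex, and fast limb to ensure group balance". It adds "A predefined list of participant numbers with corresponding randomized assignments will be generated prior to enrollment". No strata, age bands, block sizes or minimisation rule is named. In the text, the fast belt is tied to the more affected leg (section III.D.2), and no counterpart is given for neurotypical controls.

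**Covariates.** Age, sex and fast limb are not in the main models. Section V.C says instead "Separate regression models will be conducted to assess the influence of demographic covariates on primary outcome models". Fast limb is not a demographic variable and has no stated place in any analysis.

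**The concern.** A model with visit and TENS as within-person factors, plus a participant random effect, needs at least two observations per participant. Savings is already the difference between the two visits, so that structure has been used up in forming the outcome. As written, the analysis of the retention hypothesis cannot be run, and the analyst would have to choose a replacement that the SAP does not give, possibly with data in hand. A replacement could also be reported as separate evidence on retention when it repeats the TENS test on adaptation rate.

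The allocation statements conflict as well. Simple randomisation imposes no balance, whereas counterbalancing is a restriction. A reader cannot tell which was used, or how traits learned at screening were balanced by a list made before enrolment. Where a factor is balanced by design, the usual practice is to carry it into the main model, and here it is not.

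**Working it through.** **The plan's own figure.** The only calculated figure is 10 per group in section II.B.3 (effect size 1.01, alpha 0.05, power 0.8). A two-sided paired t-test gives power 0.811 at n=10 and 0.756 at n=9, so 10 is reproduced. Nothing below changes it.

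**Inputs.** 30 PwMS and 20 controls (section II.A), two visits, two TENS orders. The TENS Protocol text in section III.D.2 has 30 controls; the n=30 figures would then apply to both groups.

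**1. Adaptation rate.** Rows: 50 × 2 = 100. Fixed-effect columns: 2 × 2 × 2 = 8, rank 8. This model can be fitted. With ±1 coding, visit × TENS is constant within a participant and separates the two orders, so that term is sequence.

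**2. Savings.** Rows: 50, one per participant. Code each row by visit 2:
- visit is constant and equals the intercept, so group × visit equals group;
- TENS is the visit 2 condition, which is sequence; visit × TENS is the same column;
- group × TENS and group × visit × TENS are both group × sequence.

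The 8 columns have rank 4: intercept, group, sequence, group × sequence. With one row per participant, the variance of a savings value is the random-intercept variance plus the residual variance, and only the sum can be estimated.

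**3. What the estimable model tests.** Let π be the visit effect and τ the TENS effect on adaptation rate.
- OFF then ON: mean savings = π + τ.
- ON then OFF: mean savings = π − τ.
- Difference between sequences = 2τ.

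This was checked on a simulated complete data set with uneven splits (17:13 and 8:12). The sequence coefficient for savings was 1.1308, and the visit-adjusted TENS effect on adaptation rate was 0.5654, exactly half. Both had t = 2.548 on 50 − 4 = 46 degrees of freedom, so they are the same test. If TENS at visit 1 left a lasting gain λ at visit 2, the ON-then-OFF mean would be π − τ + λ and the contrast 2τ − λ. Retention and the direct TENS effect are therefore not separated.

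**4. Allocation, if the section II.B.4 rule is used.** With k of n in one sequence, the variance relative to an even split is (1/k + 1/(n−k)) / (4/n). Averaged over Binomial(n, 0.5), excluding empty sequences:

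| | n=20 | n=30 |
|---|---|---|
| Mean variance ratio | 1.060 | 1.037 |
| Uneven split considered | 14:6 | 20:10 |
| Probability of that split or worse | 0.115 | 0.099 |
| Variance ratio at that split | (1/14+1/6)/(2/10) = 1.190 | (1/20+1/10)/(2/15) = 1.125 |

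The section V.C rule cannot be evaluated, because its method is not stated.

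**5. Covariates.** Effects of age, sex and limb that are the same at both visits cancel from visit 2 minus visit 1. In a simulated trial with a 0.5 SD age imbalance between sequences, raising the age slope from 0 to 5 left the savings contrast at −0.1066 and the TENS effect at −0.0533. The sequence contrast moved from −0.118 to 2.383. In the mixed model, adding the three factors left TENS at −0.107 (SE 0.197) and cut the TENS × visit SE from 0.807 to 0.587.

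For between-participant terms, the variance ratio (adjusted over unadjusted) is (1 − R²)(N − 3)/(N − k − 3), with N = 50 and k = 3 covariates, i.e. (1 − R²) × 47/44. It is 1.068, 0.855 and 0.748 for R² of 0, 0.2 and 0.3. These R² values are assumptions; the documents give none.

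**The case against.** **The allocation conflict barely touches the hypotheses.** This stands. Stable factors cancel from both the TENS effect and savings. Only the group and sequence terms and the ON versus OFF comparison within a visit are exposed. That last comparison arises only if an interaction is significant: "Post-hoc comparisons will be conducted using estimated marginal means (EMM) to further investigate significant main effects and interactions".

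**A reader might infer that omitting the covariates inflates false positives.** The documents do not support this. In simulation, at least one factor differs by 0.5 SD or more between sequences in about 22% of trials. In those, the unadjusted sequence test rejects falsely 7.0–7.6% of the time at an assumed R² of 0.2, and 8.6–9.4% at 0.3. In the remaining trials it rejects a little over 4% of the time. Over all trials the rate is about 5%, so adjustment is a matter of precision.

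**A reader might infer that a list made before enrolment can never deliver the stated balance.** That goes too far. Separate numbered lists by stratum can be prepared in advance; the plan simply does not name the strata. Nor is minimisation needed.

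**A reader might also read bias into the unmasked design, with concealment of the next assignment not described.** Every participant receives both conditions, so foreknowledge could alter only who enters which sequence. No consequence has been shown.

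**Covariates are partly covered.** The demographic regressions would presumably include age and sex, and controls are matched on both. But separate regressions do not adjust the main models, and fast limb remains outside every analysis.

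None of this answers the savings defect.

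**Conclusion.** The savings analysis is wrong as written: 4 of 8 fixed-effect columns are estimable and the random effect is not identified. This follows from the definition of savings alone and needs no assumption about the data or the allocation method. A stated hypothesis therefore has no analysis that can be run. The natural replacement adds no evidence beyond the TENS test on adaptation rate when data are complete.

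The allocation conflict is genuine current text but modest in effect. If simple randomisation was used, the average cost is 6.0% (n=20) and 3.7% (n=30) in variance, and the TENS estimate is not biased. It would be shifted only by an unbalanced factor that alters the visit-to-visit change, and savings would then shift in proportion.

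Covariate adjustment is an inexpensive improvement for the group and sequence terms and does not correct an error. Its benefit depends on an R² the documents do not give.

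**What to change.** 1. **Savings (should be changed).** In section V.C, remove savings from the mixed-model and repeated measures ANOVA sentences. State that savings is analysed by an ordinary linear model with group, sequence and group × sequence, without a random effect. Add that its sequence contrast is twice the visit-adjusted TENS effect on adaptation rate and so is not an independent test of retention. Cost: a sentence or two.

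2. **Allocation (reconcile).** Delete the word simple in section II.B.4 and state one restricted 1:1 scheme, run separately within PwMS and within controls, in both sections. Permuted-block lists by named strata, prepared in advance, keep the SAP's predefined list; minimisation is an option that must be run at each enrolment. State how fast limb is determined in controls. Strata will be small: sex × limb × two or three age bands gives 8 to 12 cells, or 30/8 = 3.8 down to 30/12 = 2.5 PwMS and 20/8 = 2.5 down to 20/12 = 1.7 controls per cell. Blocks must therefore be short. If allocation has begun, which the documents do not say, record the rule actually used. The control count (20 or 30) needs separate reconciliation.

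3. **Covariates (cheap improvement).** Add age and sex, and fast limb once it is defined for controls, as fixed effects in the adaptation-rate and HbO beta models. Cost: three degrees of freedom, or about 7% more between-participant variance if the factors explain nothing.
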